FOR QUALITATIVE DATA	19
4.10 THE NUMBER OF PARTICIPANTS	19
5.0 PHASE 2: BIOLOGIC PRIMING STUDY	19
5.1 STUDY AIMS	19
5.2 PRIMARY OBJECTIVES	20
5.3 INCLUSION CRITERIA	20

5.4	EXCLUSION CRITERIA	20
5.5	RECRUITMENT AND CONSENT	21
5.6	DATA COLLECTION METHOD	21
5.7	DESCRIPTION OF STATISTICAL METHODS	21
5.8	THE NUMBER OF PARTICIPANTS	21
5.9	THE LEVEL OF STATISTICAL SIGNIFICANCE	22
5.10	WITHDRAWAL CRITERIA FOR BOTH PHASE ONE AND PHASE TWO	22
6.0	ETHICAL AND REGULATORY CONSIDERATIONS / ROLE OF SPONSOR	22
6.1	ASSESSMENT AND MANAGEMENT OF RISK	22
6.2	RESEARCH ETHICS COMMITTEE (REC) AND OTHER REGULATORY REVIEW & REPORTS	22
6.3	REGULATORY REVIEW & COMPLIANCE	23
6.4	PROTOCOL COMPLIANCE	23
6.5	DATA PROTECTION AND PATIENT CONFIDENTIALITY	24
6.6	INDEMNITY	24
6.7	ACCESS TO THE FINAL STUDY DATASET	24
7.0	REFERENCES	26
APPENDIX 1: GANTT CHART		27
APPENDIX 2: NICE DEFINITION OF HIGH DOSE INHALED CORTICOSTEROIDS		28

Glossary of Abbreviations

AE	Adverse event
AR	Adverse reaction
CI	Chief Investigator
CRF	Case Report Form
CT	Clinical Trials
DMC	Data Monitoring Committee
GCP	Good Clinical Practice
GP	General Practitioner
ICF	Informed Consent Form
ICH	International Conference of Harmonisation
NHS	National Health Service
NRES	National Research Ethics Service
PI	Principal Investigator
PIS	Participant/ Patient Information Sheet
R&D	NHS Trust R&D Department
REC	Research Ethics Committee
SAE	Serious Adverse Event
SAR	Serious Adverse Reaction
SmPC/SPC	Summary of Products Characteristics
SOP	Standard Operating Procedure
TMF	Trial Master File
TSG	Trials Steering Group
SAQ	Severe Asthma Questionnaire
ACQ	Asthma Control Test
GINA	Global Initiative for Asthma
GRCQ	Global Rating of Change Questionnaire

Keywords

Severe Asthma

Biologic treatment

Body Reprogramming

Study Summary

Title	Body Reprogramming as an adjunct to biologic administration in patients with symptomatic Severe Asthma: a feasibility study
Design	A feasibility study of Body Reprogramming (BR) in 2 patient groups one as an addition to normal treatment and one provided before starting a biologic treatment
Aims	
 • To assess the feasibility and acceptability of BR to people with severe asthma, • Using patient and other feedback to adapt and optimise the intervention for people with severe asthma.
Outcome Measures	
 • Number and percentage of participants taking part and completing the course including those completing the following questionnaires 
 ○ Severe Asthma Questionnaire (SAQ) ○ General Symptom Questionnaire (GSQ) or GSQ-Asthma (GSA-A) ○ Positive and Negative Affect Schedule (PANAS) ○ Asthma Control Questionnaire (ACQ) ○ Global Rating of Change questionnaire (GCRQ) • Attendance to Body Reprogramming Zoom calls • Feedback received using the Friends and Family Test (FFT) 
Qualitative data from the focus groups or interviews analysed using thematic analysis concerning participants' experiences of Body Reprogramming.

Population	Patients with symptomatic severe asthma attending the regional severe asthma clinic in RD&E Hospital Devon.
Eligibility	
Phase 1
 
Patient has severe asthma as per ERS/ATS definition and is receiving high dose inhaled corticosteroids as defined by NICE (Appendix 2)
 
AND
 
Eight or more non-respiratory symptoms per week recorded on the GSQ
 
Phase 2
 
Patients with severe asthma who have been approved to commence a biologic treatment for their severe asthma

Duration	15 months
Timelines	See Gantt Chart (Appendix 1)

1. INTRODUCTION

1.1 Background

Research and clinical experience show that severe asthma is a polysymptomatic disease and that the contributions to health related quality of life (HRQoL) disutility is complex (1). As such, patients often live with a number of symptoms (related to both the disease and treatment) and including a high level of extra-pulmonary symptoms, all of which actively contribute to HRQoL deficit (2).

Our research demonstrates that the HRQoL deficit in patients with severe asthma is affected by both pulmonary and extra-pulmonary symptoms (e.g. mental fog, fatigue, unexplained pain) that contribute equally to the total HRQoL deficit (3). We have also shown that the frequency and severity of extra-pulmonary symptoms in severe asthma are similar to those in patients diagnosed with syndromes of medical unexplained symptoms such as fibromyalgia and chronic fatigue syndrome (4), two conditions where outcome is improved by lifestyle change. The current Covid-19 pandemic places additional lifestyle burden on patients with severe asthma as these patients fall into the high risk category.

1.2 Rationale for Current Study

When assessing the impact of management and treatment interventions aimed at improving HRQoL, it is important to look beyond the lung. In a cross-sectional study of severe asthma, we found that the frequency of extra-pulmonary symptoms significantly increased with the cumulative burden of systemic corticosteroids. However, those patients on biologic treatments had lower symptom scores irrespective of their systemic steroid burden (4).

We hypothesize that a specific intervention aiming to optimising patient knowledge on disease management, physical activity, relaxation (5) and other psychological and biological lifestyle changes that increase well-being and mood, may lead to improved self-management. Severe asthma patients lack any form of rehabilitation provision analogous to pulmonary rehabilitation, which is an evidenced-based education and exercise programme for people with COPD and has additional benefits on top of drug therapies (6). Indeed evidence shows that pulmonary rehabilitation should be provided prior to stepping up drug treatments in COPD , leading to the hypothesis that a similar provision for severe asthma patients prior to

starting new treatments such as biologics would enhance response to treatment. Furthermore there is emerging evidence that pre-habilitation improves outcomes in high risk patients undergoing surgery and is now being recommended to improve resilience in the face of the SARS-CoV-2 pandemic (7). BR may well act as a strategy to promote resilience to Coronavirus amongst an at risk group of severe asthma patients.

We hope to see greater HRQoL improvements from severe asthma patients who have been “primed” by an education and behaviour change programme when they start biologics. Biologic therapies have a highly specific mode of action and may therefore interact positively with any reduction in systemic inflammation resulting from lifestyle improvement. We have provided a detailed theoretical rationale for potential mechanisms (8).

1.3 Patient and Public involvement (PPI)

The original Body Reprogramming course structure and narrative was developed for and with patients with fibromyalgia (9). People with fibromyalgia have a wide variety of symptoms many of them shared with people who have severe asthma (4). The present study is to examine the feasibility of an adaptation of the original course, an adaption specifically designed for people with severe asthma.

The adapted course content consists of four half hour sessions designed to be presented via Zoom video call. The content of the course (Appendix 6) was discussed with a group of 8 severe asthma patients and edited based on patient feedback. While most of the patients were happy to take part in an intervention run in groups, some interpreted the group nature of Body reprogramming as a form of “group therapy” where problems were discussed amongst the attendees. The wording of the patient information leaflet and course information was amended to clarify that Body Reprogramming is considered an educational intervention where participants attend a series of presentations. It is now worded to make clear that patients can choose whether or not they say anything during the presentations. They have the opportunity to ask questions but there is no requirement for active participation.

Originally, Body Reprogramming was delivered in person over 7 weeks at a patients treating hospital. However, in response to the UK national Covid 19 regulations and social distancing rules, this study will be delivered via the Zoom video call platform. The original 7-week course

was discussed with asthma patients who suggested that a shorter 4-week course would be more appropriate for an online intervention and that each course should last no longer than about 30 minutes.

2. Summary of Body Reprogramming

Body Reprogramming (BR) is a non-drug, multi-component intervention originally developed in Plymouth for fibromyalgia patients (see www.bodyreprogramming.org) and provided to patients through the NHS with direct referral from a GP in Devon and Cornwall. BR is applicable to any patients whose polysymptomatic presentation cannot be explained by current disease models (10). The aim of BR is to improve general health and well-being by evidence-based lifestyle change. The unique feature of BR is a theoretical model that personalises lifestyle advice to the particular patient and provides patients with a narrative that explains how and why the changes can produce benefit.

The theoretical model proposes that symptoms result from a network of biological symptom causing mechanisms (11). The extra-pulmonary symptoms of severe asthma can be explained by inflammatory mediators being part of this network that include, but are not limited to, non-specific pro-inflammatory cytokines (8). Patients are provided with a simplified version of the theory based on an analogy of 'hardware' and 'software' faults in a computer (9).

3. Study Design

This is an unblended observational study, single-site feasibility study in two phases:

Phase 1 Proof of concept.

The aim of this study is to assess the feasibility and acceptability of BR, whilst optimising the intervention for people with severe asthma.

Phase 2 Biologic priming feasibility study.

Patients expected to start a biologic treatment for their severe asthma will be invited to take part in a BR course.

Participating sites include:

- Royal Devon and Exeter Hospital NHS Foundation Trust, Exeter, UK (RD&E)

4.0 Phase 1: Proof of Concept, Four-Week Trial of BR and Post-Trial Focus Groups or Interviews

4.1 Study Aims

- To assess the feasibility and acceptability of BR to people with severe asthma in a feasibility study with remote delivery via on-line groups.
- To adapt and optimise the intervention for people with severe asthma.

4.2 Primary objectives

Four-week trial of BR

- To assess patients' willingness to attend BR and engage with the intervention as measured by course attendance and by their written feedback.
- To record the user experience when participating in the trial.
- To assess patient's willingness to complete a series of questionnaires
- To get patient feedback on the appropriateness of the questionnaires for assessing improvement in larger future studies

Post-trial focus groups or interviews

- To gain qualitative feedback on patients experience of BR following their participation in the four-week trial.
- To assess the acceptability of BR for people with severe asthma.
- To understand the barriers to attending BR by speaking those who did not attend the course.

- Using all the data from participants we will adapt the BR programme before commencing phase two.

4.3 Inclusion criteria

- Aged ≥ 18 years attending the regional specialist severe asthma service in Royal Devon and Exeter hospitals.
- Diagnosed with severe asthma as per ERS/ATS definition.
 - Requiring high dose inhaled corticosteroids (NICE definition of high dose ICS, Appendix 2).
- Eight or more non-respiratory symptoms per week (approximately 60% of patients with severe asthma have a moderate or high extra-pulmonary symptom burden) as measured by the General Symptom Questionnaire (12).

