4.4 Exclusion criteria

- Unable or unwilling to partake.
- In the opinion of the patient's treating physician, the patient has another condition which is significantly impairs their ability to take part in the BR.
- No access to the internet or appropriate IT equipment

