This questionnaire contains 7 items and takes into consideration FEV1% predicted and daily use of rescue bronchodilator. Patients respond to 7 items concerning their symptom severity on a 0-6 scale (0 = no impairment, 6 = maximum impairment) (14). The questionnaire asks patients to assess their symptoms over the last week.

Note: the included questionnaires are available and validated in the majority of European languages and many non-European ones. However, if a participant requires a translation of a questionnaire that is not available, they will not be asked to complete the particular questionnaire.

Post course questionnaires

Global Rating of Change Questionnaire – Phase one (Appendix 12)

This scale will be used by participants to indicate how much better they feel since commencing a BR. The 11-point scale ranges from -5 (a great deal worse) to 5 (A great deal better) (15). The time scale is between before the start of treatment and the current assessment.

All questionnaires are presented in paper and pencil format, to be self-completed by the patient but with support if needed.

Friends and Family Test (FFT) (Appendix 13)

This is a one question questionnaire used throughout the NHS to assess patient's thoughts on a health service they regularly use. The question we will use in the FFT asks "We would like you to think about your recent experience of our Body Reprogramming. How likely are you to recommend Body Reprogramming to friends and family if they needed a similar service?

" Participants will respond on a 5 point scale from "Extremely Unlikely" to "Extremely Likely".

Questionnaire completion

Data on the number and percentage of questionnaires collected at the two time points will be recorded. This data will inform participants' willingness to complete the above questionnaires.

Post-trial focus groups or interview

Focus groups will consist of 3-6 participants and moderated by one of the members of the research team with qualitative research experience (LC, MH, JL). Two focus groups will be

conducted in total, and will explore the experience of participants after participating in a four-week trial of BR.

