5.3 Inclusion criteria

- Diagnosed with severe asthma as per ERS/ATS definition.
 - Requiring high dose inhaled corticosteroids (NICE definition of high dose ICS, Appendix 2).
- Patients with severe asthma who have been approved for biologic treatment according to national guidance and have been assessed by a multi-disciplinary team will be offered the intervention pending starting their biologic treatment.
- Patients with eight or more non-respiratory symptoms per week as measured by the GSQ.

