5.4 Exclusion criteria

- Unable or unwilling to take part.
- Participated in phase 1 of the study
- In the opinion of the patient's treating physician, the patient has another condition which is significantly impairs their ability to take part in BR.

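### Phase 1 sets no condition on biologic status and records no biologic start dates or in-course starts, so drug effect could enter its score changes and the between-phase comparison unidentified

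*Combined protocol and SAP*

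**What the plan says.** The Study Summary describes two patient groups, "one as an addition to normal treatment and one provided before starting a biologic treatment". Biologic timing is what distinguishes them.

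The Phase 1 inclusion criteria (4.3) are adult age and attendance at the regional severe asthma service, "Diagnosed with severe asthma as per ERS/ATS definition" with a high-dose inhaled corticosteroid requirement, and eight or more non-respiratory symptoms per week on the GSQ. The exclusions (4.4) cover willingness or ability, another impairing condition in the treating physician's view, and "No access to the internet or appropriate IT equipment". Neither list mentions being on, newly started on, or awaiting a biologic. Phase 2 (5.3) repeats the clinical criteria and adds approval for a biologic; its patients "will be offered the intervention pending starting their biologic treatment".

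Section 4.7 has a researcher extract current drug treatment from the clinical records at baseline. It lists no start date and no later update. Questionnaires are completed in the first and last week of the course, and 5.6 keeps the same time points for Phase 2.

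Section 4.9 plans pre-post mean differences for all scores, plus an analysis of covariance on baseline score and disease severity. Section 5.7 applies the same methods to Phase 2 and adds a look for outcome differences between the phases. The rationale (1.2) reports, from a cross-sectional study, that "those patients on biologic treatments had lower symptom scores irrespective of their systemic steroid burden".

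**The concern.** The between-phase comparison makes sense only if it is known who was on a biologic, and since when. Under 4.3 and 4.4, a clinic patient who had a first biologic dose last week, or who will have one in week two, can enter Phase 1. Any early drug response in that patient is then counted in a Phase 1 score change.

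The outcomes at stake are the ones that the protocol itself links to biologics, namely symptom scores and through them quality of life. The model in 4.9 has no biologic term. Because the Phase 2 course is offered before the biologic, Phase 1 could even contain more drug effect than Phase 2, which would blur the contrast that 5.7 wants to describe. The score changes are meant to inform the design of later studies, so an unrecognised drug contribution would be carried forward.

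**Working it through.** **Could the plan identify these patients afterwards?** Three situations need to be separated.

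| Patient at Phase 1 entry | Adds drug effect to the pre-post change? | Identifiable from the planned data? |
|---|---|---|
| Awaiting a biologic, no start during the course | No | Not needed |
| Started or switched shortly before the first questionnaire | Possibly | Seen as a biologic user at baseline, but not as a recent starter, because no start date is listed |
| Starts or switches between first and last questionnaire | Possibly | No, because drug treatment is recorded at baseline only |

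Section 5.10 does not close the gap. It re-assesses eligibility when health or diagnosis changes, but a biologic start breaches no Phase 1 criterion.

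**The plan's own figure.** Section 4.10 states 12–14 recruits, 10% withdrawal and at least 10 completers. Check: 12 × 0.90 = 10.8 and 14 × 0.90 = 12.6, so the figure is reproduced. There is no power calculation, effect size or SD to reproduce, and 5.9 gives the significance level as not applicable.

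**Weight of one patient.** 1/14 = 7.1% and 1/12 = 8.3% of the cohort. If only 10 people supply both questionnaires, it is 1/10 = 10%.

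**Shift in the mean change.** With *k* starters among *n* participants and a drug effect *d* realised within the four weeks, shift = (*k*/*n*) × *d*. The documents give neither *k* nor *d*, so both are assumed here: *k* = 3 and *d* = 0.5 to 1.0 SD.

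| *n* | *k*/*n* | *d* = 0.5 SD | *d* = 1.0 SD |
|---|---|---|---|
| 12 | 3/12 = 0.250 | 0.125 SD | 0.250 SD |
| 14 | 3/14 = 0.214 | 0.107 SD | 0.214 SD |

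The range is 0.11–0.25 SD. With one starter it is 0.036–0.083 SD (from 0.5/14 to 1.0/12).

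**Chance of enrolling at least one such patient.** If a share *q* of eligible patients is newly on, or about to start, a biologic, P = 1 − (1 − *q*)^*n*. The documents do not give *q*.

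| Assumed *q* | *n* = 12 | *n* = 14 |
|---|---|---|
| 5% | 46% | 51% |
| 10% | 72% | 77% |
| 20% | 93% | 96% |
| 30% | 99% | 99% |

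**Scale against sampling error.** For a difference between two phase means of *n* each, the standard error is √(2/*n*) in SD units: √(2/12) = 0.41 and √(2/14) = 0.38. If the drug effect is expressed in the same SD (that of the score change), the illustrated shift is below one standard error: 0.25/0.41 ≈ 0.6 at most and 0.107/0.38 ≈ 0.3 at least.

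**The case against.** The strongest reply is that this is a feasibility study. The Phase 1 objectives (4.2) concern attendance, feedback, user experience, questionnaire completion, acceptability and barriers, and a biologic start hardly touches these. Nothing is tested, and an uncontrolled pre-post change in 12–14 people cannot isolate an effect of Body Reprogramming in any case. Course adaptation after Phase 1 concerns practical matters and narrative (4.9), which drug benefit is unlikely to distort. Broad eligibility is defensible too: 5.2 plans a booklet for people starting or already on a biologic, so their views are relevant. Baseline drug treatment already shows who is on a biologic, and a full analysis plan is still to be written. The size of the shift rests on assumed inputs, and 1.2 offers only a cross-sectional association, not a four-week response.

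Most of that stands, and it limits the point to the score changes and the phase comparison. What does not stand is reliance on the later analysis plan. It can describe results by biologic status only if start dates and in-course starts have been recorded.

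Three stronger readings are tempting but not supported:

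- *Every biologic candidate enrolled in Phase 1 is lost to Phase 2.* Section 5.4 does exclude anyone who "Participated in phase 1 of the study". But 4.2 has the programme adapted before Phase 2 begins, so the phases are consecutive. A candidate is lost only if still untreated when Phase 2 opens. Anyone who starts the drug in between no longer fits 5.3, whether or not they joined Phase 1. The size of the approved pool is not stated.
- *Patients awaiting a biologic should therefore be excluded from Phase 1.* Waiting adds no drug effect. With consecutive phases, such a rule could shut these patients out of both.
- *The Phase 1 Global Rating of Change measures change caused by the course alone.* It asks participants to "indicate how much better they feel since commencing a BR", and 4.8 gives the period covered. That is a time anchor, not a causal attribution.

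**Conclusion.** The point holds in a limited form. Phase 1 sets no condition on biologic status, and the planned data cannot distinguish a recent starter from an established user or reveal a start during the course. Drug effect could therefore enter the Phase 1 score changes and the comparison in 5.7, and could not be separated later from the study data.

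Each affected patient carries 7–8% of the cohort mean. The 0.11–0.25 SD illustration needs three starters and a 0.5–1.0 SD response within four weeks, all assumed; with no starters there is no shift. The conclusions on feasibility and acceptability are not at risk. This is a cheap improvement worth making before enrolment, not a flaw that undermines the study.

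**What to change.** - **Section 4.7, and 5.6 for Phase 2:** record the start date of any biologic in use at baseline, and any biologic start or switch, with its date, between the first and last questionnaires.
- **Sections 4.9 and 5.7:** report the score changes and the phase comparison descriptively, with and without patients who recently started or switched, or by biologic status. State in the analysis plan, before the data are examined, what period before the first questionnaire counts as recent.
- **Section 5.6:** reconcile the Phase 2 rating-of-change wording, which refers to both the course and a biologic, with a last-week questionnaire in a course offered before the biologic starts. The recorded dates would show which participants had begun the drug by then.

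Eligibility stays as it is, so no recruits are lost and patients established on a biologic remain in Phase 1. The cost is one record item, taken from records that the researcher already consults at baseline and checked once more at the end of the course, and one extra descriptive table. With 12–14 patients per phase, the split will be descriptive only.
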